**17.3.2. Exploratory Questions**

The following questions are about the hair on your entire scalp (including the front, sides, top, and back of your head). Please answer these questions assuming that you are not wearing a wig.

Circle or mark one answer for each question.

1. Overall, how satisfied are you with your hair?
	
Very Satisfied       Satisfied       Neutral       Unsatisfied       Very Unsatisfied 

2. How satisfied are you with the fullness/thickness of your hair?
	
Very Satisfied       Satisfied       Neutral       Unsatisfied       Very Unsatisfied 

3. How satisfied are you with the amount of hair on your scalp?
	
Very Satisfied       Satisfied       Neutral       Unsatisfied       Very Unsatisfied 

4. How satisfied are you with the way your hair covers your scalp?
	
Very Satisfied       Satisfied       Neutral       Unsatisfied       Very Unsatisfied 

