3. GENERAL ANALYSIS AND REPORTING CONVENTIONS

The following is a list of general analysis and reporting conventions to be applied to this study, unless otherwise specified.

All data displays (tables, listings, and figures) will have a header showing the sponsor company name, protocol number, page number, and display status (i.e. “DRAFT” or “FINAL”), as well as a footer indicating path, file name, and run date/time. Summary tables and data listings will be summarized by treatment and overall, as appropriate. All data collected per-protocol and all derived variables will be listed.

Categorical variables will be summarized using counts (n) and percentages (%) and will be presented in the form “n (xx.x).” If a count is 0, 0% will be shown for the percentage. If a percentage is 100%, 100% will be shown with no decimal place. To ensure completeness, summaries for categorical variables will include all categories, even if no patients had a response in a particular category. Unless otherwise specified, the denominator for each percentage will be based on the number of patients in the population being summarized (header n). If missing values are present, counts will be shown but will not be included in percentage calculations.

Continuous variables will be summarized using mean, standard deviation (SD), minimum, maximum, median, and number of patients. The mean and median will be reported to an additional level of precision than the original observations, and the SD will be reported to two additional levels of precision than the original observations. The minimum and maximum will be the same precision as the original data. In general, any calculated values, such as those due to unit conversion, will be rounded to the same number of decimal places as the original data.

All statistical tests will be 2-sided with a significance value of 0.05. Testing will be performed only for the Treatment Period. Estimates and confidence intervals will be reported to 1 more decimal than the original data. P-values will be reported to 3 decimal places.

Summary tables and data listings:

- No preliminary rounding will be performed; rounding will only occur after analysis.
- Data from patients excluded from an analysis population will be presented in the data listings but will not be included in the calculation of summary statistics, where applicable.

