8.4 Analysis Methods

All statistical tests will be 2-sided with a significance value of 0.05. Testing will be based on the Efficacy population and performed only for the Treatment Period. An analysis of the primary efficacy endpoint and exploratory SALT endpoints will also be performed for the Per Protocol population. The final efficacy analysis will be conducted when all patients in the 12 mg cohort have completed Week 24. The placebo groups from all 3 cohorts will be pooled and compared to each active dose (4 mg, 8 mg, and 12 mg) individually. Active doses, 4 mg, 8 mg, and 12 mg, will also be compared. There will be no adjustment for multiple treatment group comparisons in this dose-ranging Phase 2 study.

Table 8-1 gives an overview of the analysis methods that will be used for each of the efficacy variables.

Table 8-1 Efficacy Variables and Analysis Methods

Efficacy Variables	Collection Times	Method
Primary		
Responder Analysis SALT (50% relative reduction)	Baseline, Week 24	χ^2 Test
Exploratory		
Responder Analysis SALT (50% relative reduction)	Baseline, Week 4, 8, 12, 16, 20	χ^2 Test
Responder Analysis SALT (75%, 90%, and 100% relative reduction)	Baseline, Week 4, 8, 12, 16, 20, 24	χ^2 Test
SALT (≤ 10 , ≤ 20 , ≤ 25 absolute score)	Baseline, Week 4, 8, 12, 16, 20, 24	χ^2 Test
SALT (absolute change)	Baseline, Week 4, 8, 12, 16, 20, 24	MMRM
SALT (relative change)	Baseline, Week 4, 8, 12, 16, 20, 24	MMRM
SALT (absolute score)	Baseline, Week 4, 8, 12, 16, 20, 24	MMRM
Clinician VAS-S (percent change)	Baseline, Week 12, 24	ANCOVA
Patient VAS-S (percent change)	Baseline, Week 12, 24	ANCOVA
CGI-I	Week 12, 24	χ^2 Test
CGI-I Responder (“Very Much/Much Improved” and “Much/Very Much Worse”)	Week 12, 24	χ^2 Test
PGI-I	Week 12, 24	χ^2 Test
PGI-I Responder (“Very Much/Much Improved” and “Much/Very Much Worse”)	Week 12, 24	χ^2 Test
AASIS	Baseline, Week 24	Descriptive Statistics
Exploratory Questions	Baseline, Week 24	Descriptive Statistics
Responder Analysis, Exploratory Questions, Satisfied v. Unsatisfied	Baseline, Week 24	χ^2 Test

χ^2 = Chi-Squared Test; ANCOVA = analysis of covariance; CMH = Cochran-Mantel-Haenszel; MMRM = mixed-effect model for repeated measures

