A χ^2 trend test will be used to analyze CGI-I and PGI-I between treatment groups overall. Responses for PGI-I and CGI-I categorized as achieving “Very Much/Much Improved” or “Much/Very Much Worse” will also be compared between treatment groups with the χ^2 test. Descriptive statistics and by-patient data listings will also be presented for the 7 response categories for each assessment.

Mean and mean change from baseline for total AASIS score will be reported. Number and percentage of subjects in each response category of AASIS will also be summarized. Individual responses will be listed in categories of “Severity” and “Interference”.

The exploratory questions will be summarized with descriptive statistics at baseline and Week 24, and will be listed in the by-patient data listings. Responses will be categorized as “Satisfied” (including responses of “Very satisfied” and “Satisfied”) and “Unsatisfied” (including responses of “Unsatisfied” and “Very unsatisfied”) and presented as a 2 x 2 shift table from baseline to Week 24, compared with a χ^2 Test by cohort.

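### The satisfaction responder analysis has no cell for the Neutral answer, so, read literally, it drops patients because of their Week 24 response

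*SAP*

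**What the plan says.** - **The questionnaire.** Protocol 17.3.2 has four questions, the first being "Overall, how satisfied are you with your hair". Each offers Very Satisfied, Satisfied, Neutral, Unsatisfied and Very Unsatisfied.
- **The two classes.** SAP 8.4.2 defines Satisfied as "including responses of “Very satisfied” and “Satisfied" and Unsatisfied as "including responses of “Unsatisfied” and “Very unsatisfied". Neutral is named in neither.
- **The layout and test.** Answers are put into these two classes "and presented as a 2 x 2 shift table from baseline to Week 24", then "compared with a χ^2 Test by cohort". SAP Table 8-1 carries the same analysis as "Responder Analysis, Exploratory Questions, Satisfied v. Unsatisfied", by chi-squared test.
- **The general convention.** SAP section 3 says that, unless otherwise specified, "the denominator for each percentage will be based on the number of patients in the population being summarized (header n"), and takes only missing values out of percentages. It does not call Neutral missing.
- **Other displays.** SAP 8.4.2 also calls for descriptive summaries of the questions at baseline and Week 24 and for by-patient listings. SAP section 3 requires categorical summaries to show every category.
- **Origin.** Protocol 12.4.2 planned an analysis of covariance of change from baseline for these questions. SAP section 12 records the move to a chi-squared test.

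**The concern.** A table with two rows and two columns labelled Satisfied and Unsatisfied cannot hold a Neutral answer. Neither document says where that answer goes. Taken as written, a patient who is Neutral at either visit is absent from the tested table.

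The Week 24 loss is the one that matters for inference, because it selects patients on an outcome measured after randomisation. Someone who moves from Very Unsatisfied to Neutral is neither a responder nor a non-responder but is simply removed. If treatment changes how often patients answer Neutral, the remaining patients no longer form comparable groups. The satisfied proportion, and any p-value comparing arms, then reflects the Neutral rates as well as satisfaction.

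Patients who are Neutral at baseline are also unplaced. That loss depends on a pre-treatment answer, so it reduces the numbers and narrows the population but is not a post-randomisation bias.

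**Working it through.** **Inputs.** The plan states no expected rate or power for this endpoint, so there is no figure of its own to reproduce. The power statement in SAP 2.6 concerns the primary SALT endpoint. I take only its group size, 28 per arm, and the two-sided 0.05 level. All counts and Neutral shares below are assumptions. S, N and U are the numbers satisfied, neutral and unsatisfied at Week 24, n = S+N+U, and q = N/n.

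**Step 1: effect on one arm.** Keeping Neutral in the denominator gives S/n. Dropping it gives S/(S+U) = (S/n)/(1-q). For a true 30% satisfied:

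- q = 10%: 0.30/0.90 = 33.3%
- q = 20%: 0.30/0.80 = 37.5%
- q = 30%: 0.30/0.70 = 42.9%
- q = 40%: 0.30/0.60 = 50.0%

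**Step 2: effect on a comparison of arms.** This supposes that the test contrasts active with pooled placebo at Week 24 (uncorrected chi-squared).

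| Case | Active S/N/U | Placebo S/N/U | Neutral dropped | p | Neutral kept as not satisfied | p |
|---|---|---|---|---|---|---|
| A | 10/10/8 | 5/3/20 | 10/18 = 55.6% v 5/25 = 20.0% | 0.016 | 35.7% v 17.9% | 0.131 |
| B | 10/3/15 | 5/12/11 | 10/25 = 40.0% v 5/16 = 31.3% | 0.570 | 35.7% v 17.9% | 0.131 |
| C | 7/14/7 | 7/2/19 | 7/14 = 50.0% v 7/26 = 26.9% | 0.144 | 25.0% v 25.0% | 1.000 |
| D | 12/8/8 | 2/12/14 | 12/20 = 60.0% v 2/16 = 12.5% | 0.004 | 42.9% v 7.1% | 0.002 |

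For case A the statistic with Neutral dropped is 43 × (10×20 − 8×5)² / (18×25×15×28) = 5.82. With Neutral kept it is 56 × (10×23 − 18×5)² / (28×28×15×41) = 2.28.

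Cases A and B have the same numbers satisfied. Only the Neutral split differs, and it moves the result in opposite directions. In case C a 23-point difference appears between arms with equal satisfaction, although that table is not significant. In case D placebo has more Neutral answers yet rises by only 5.4 points, while active rises by 17.1. The relative inflation follows q (1.75 for placebo, 1.40 for active); the absolute inflation also depends on how many are satisfied.

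**Step 3: error rate.** I used 40,000 simulated trials of 28 v 28 for each setting, with 25% truly satisfied in both arms. The table gives the proportion rejecting equality of the satisfied rates.

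| Neutral share, active v placebo | Dropped | Kept |
|---|---|---|
| 40% v 10% | 16.1% | 4.8% |
| 30% v 10% | 9.2% | 4.9% |
| 20% v 10% | 6.1% | 4.9% |
| 20% v 20% | 5.2% | 4.9% |

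With equal Neutral shares the error rate stays near nominal. The distortion needs a difference in q and grows with it.

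**Step 4: the value placed on Neutral.** In case A, counting Neutral as a good outcome gives 20/28 = 71.4% v 8/28 = 28.6%, p = 0.001, against p = 0.016 with Neutral dropped. On that view, dropping Neutral hides benefit.

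**The case against.** The strongest reply is that exclusion is inferred. No sentence removes Neutral patients, and the section 3 convention would put them in the denominator: case A would then report 10/28 = 35.7% for active, not 55.6%. The table shells, which are in a separate attachment, may settle the layout. This stands as far as it goes. But the convention governs percentages, and a chi-squared statistic is built from cells. Under it, the percentages and the p-value could rest on different patients, so the text still needs settling.

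A second reply is that the analysis may not compare arms at all. A chi-squared test on a baseline-by-Week 24 table tests association between visits, and the words about cohort do not clearly name an active-placebo contrast. If every patient were Unsatisfied at baseline, one row would be empty and that test could not be computed. This also stands: the figures in Steps 2 and 3 apply only if arms are compared. Neutral is unplaced either way.

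Third, the endpoint is exploratory, and the descriptive tables and listings keep the Neutral answers visible. That limits the consequence, but it does not repair the tested table.

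A reader might go further and infer that the rule favours CTP-543 because partial regrowth leads to Neutral, or that it inflates satisfaction most in whichever arm has most Neutral answers. The documents support neither. They give no Neutral frequencies and do not link regrowth to that answer, and case D contradicts the second claim on the absolute scale.

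**Conclusion.** The gap is real: the questionnaire offers an answer for which the responder definition and the 2 x 2 layout have no place. On the literal reading, patients leave the tested table because of their Week 24 answer, and the satisfied proportion is inflated by a factor of 1/(1-q). That is 1.11 at q = 10% and 1.67 at q = 40%. If arms are compared and q differs between them, the comparison can be biased and the error rate can rise, to 16.1% in the most extreme setting examined.

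This rests on three assumptions: that Neutral is excluded, which is the literal reading and not a stated rule; that the test contrasts arms; and that the Neutral shares are in the range tried. The term inflation also presumes that Neutral counts as not satisfied. Actual size and direction are unknown. The primary SALT analysis is untouched, so this is a worthwhile and inexpensive correction to an exploratory endpoint, not a threat to the trial's main conclusion.

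**What to change.** In SAP 8.4.2 and Table 8-1, define the responder as Satisfied or Very Satisfied, against not satisfied (Neutral, Unsatisfied or Very Unsatisfied). Put every patient who answered the question at Week 24 in the denominator. Replace the 2 x 2 shift table with a 3 x 3 table (Satisfied, Neutral, Unsatisfied) from baseline to Week 24. The same edit should say which groups the chi-squared test compares.

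The cost is a sentence or two of SAP text, the Table 8-1 entry and one table shell. Satisfied percentages will be lower, possibly by a material amount: 55.6% becomes 35.7% for the active arm in case A. A move from Unsatisfied to Neutral will count as non-response, which is a judgement, but the 3 x 3 table keeps those moves visible.

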## **12.4. Analyses**

For the Treatment Period, data will be summarized by active treatment by cohort dose level versus placebo-treated patients (i.e., by treatment group). The placebo patients from the 3 cohorts will be combined for statistical comparisons to each active treatment group. All data for analysis will be listed by patient.

Continuous measures will be summarized descriptively (mean, standard deviation, median, minimum value, and maximum value) and categorical measures will be presented as number and percentage.

Additional details for statistical methods will be provided in the Statistical Analysis Plan.

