2.4 Treatment Regimens

CTP-543 will be dosed orally as tablets at doses 4 mg, 8 mg, 12 mg, or matching placebo, every 12 hours during the Treatment Period. Doses will be allocated to each cohort as follows:

- Cohort 1: 4 mg (2:1 CTP-543 4 mg : placebo)
- Cohort 2: 8 mg (2:1 CTP-543 8 mg : placebo)
- Cohort 3: 12 mg (5:1 CTP-543 12 mg : placebo)

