2.6 Sample Size Determination

There are very few studies in the literature to provide reliable estimates of active treatment or placebo response rates using SALT, or the estimate of variances around these measures, in patients with alopecia areata. Power calculations assume a 2-sided chi-squared test and significance level of 0.05 and are based on an active treatment response rate of 45% and a placebo response rate of 10%.

Although patients will be randomized in an unbalanced ratio of active drug to placebo within each cohort, the placebo patients from the 3 cohorts will be combined for statistical comparisons to each active treatment group. The first 2 cohorts will be randomized in a 2:1 ratio (active:placebo) and the third cohort will be randomized in a 5:1 ratio (active:placebo). Based on estimated completion rates, this randomization scheme is expected to provide a similar number of patients in each CTP-543 dose group and the pooled placebo group. Thus, power calculations for the comparison to placebo are based on a 1:1 treatment ratio of each CTP-543 dose group to placebo. Power calculations assume a 2-sided test and significance level of 0.05 and are based on an active treatment response rate of 45% and a placebo response rate of 10%. Based on estimated completion rates as of Amendment 4, this randomization scheme is expected to provide a similar number of patients in the 12 mg group and the pooled placebo group.

A sample size of 28 patients in the 12 mg group and 28 patients in the pooled placebo group will provide >80% power for the chi-squared test when comparing each dose group to the combined placebo group (28 active, 28 placebo). Approximately 150 patients will be randomized in order to provide 120 patients who complete treatment.

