7. MEASUREMENTS OF TREATMENT COMPLIANCE

Patients will strive for 100% compliance with the daily dosing schedule. Treatment compliance will be summarized as time on treatment as well as percent of planned dose received for each treatment group. Time on treatment will be defined as date of last dose in the treatment period minus the date of first dose in the treatment period + 1. Percent of planned dose received will be calculated for the entire treatment period as follows:

$$100 * \frac{\textit{Tablets Dispensed} - \textit{Tablets Returned}}{\textit{Tablets Expected}}$$

Tablets Expected is defined as the time on treatment multiplied by the expected number of active dose pills taken daily (x2 for the 4 mg cohort, x2 for the 8 mg cohort, and x 2 for the 12 mg cohort). Dose interruptions will be ignored in this calculation. Patient compliance and dosing exceptions will be listed in by-patient data listings.

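### SAP 8.4.2 words the chi-squared test on the satisfaction questions as a shift-table test by cohort, which is not the dose-versus-pooled-placebo comparison the SAP uses elsewhere (exploratory, low severity)

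*SAP*

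**What the plan says.** SAP 8.4.2 groups the five-point satisfaction answers into Satisfied and Unsatisfied. The result is "presented as a 2 x 2 shift table from baseline to Week 24, compared with a" chi-squared "Test by cohort". Table 8-1 lists the item as "Responder Analysis, Exploratory Questions, Satisfied v. Unsatisfied", with a chi-squared test and no statement of which groups are compared.

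The rest of the SAP sets a different pattern:

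- SAP 8.4, for efficacy testing generally: "The placebo groups from all 3 cohorts will be pooled and compared to each active dose", individually for 4, 8 and 12 mg. Active doses are also compared with one another.
- SAP Section 3: summary tables are presented by treatment. Placebo is split by cohort only in listings and is pooled in summary tables. The satisfaction shift table is planned Table 14.2.4.2, so it is a summary table.
- SAP 8.4.2, same paragraph group: the CGI-I and PGI-I tests are between treatment groups, and the SALT responder tests follow 8.4.1.
- SAP 2.4: each cohort contains both active and placebo patients, at 2:1, 2:1 and 5:1.

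SAP Section 12 declares the move from ANCOVA to a chi-squared test for these questions. It declares no departure from pooled placebo.

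**The concern.** Both dimensions of a baseline-to-Week-24 shift table are time points in the same patients. A Pearson chi-squared test on it measures association between a patient's two answers. It does not compare treatments, and it does not test net change either. Running it *by cohort* puts active and placebo patients into the same table.

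The phrase can also be read as active versus placebo within each cohort. That is a legitimate concurrent comparison, but with a much smaller comparator than the pooled group.

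At stake is one exploratory p-value per question. A programmer working from the text alone could report a number that looks like a treatment test and is not one.

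**Working it through.** **Inputs.** SAP 2.6 gives "A sample size of 28 patients in the 12 mg group and 28 patients in the pooled placebo group", 45% versus 10% SALT response, two-sided 0.05, power above 80%, and 120 completers. SAP 2.4 gives the allocation ratios. No satisfaction rates are given anywhere, so everything after step 1 is illustration.

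**1. The plan's own power figure (SALT endpoint).** Power = Φ[(d − 1.96·se0)/se1], with se0 from the pooled proportion and se1 from the separate proportions. For 28 v 28:

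- pooled proportion 0.275
- se0 = √(0.275 × 0.725 × 2/28) = 0.1193
- se1 = √(0.2475/28 + 0.09/28) = 0.1098
- power = Φ[(0.35 − 0.2339)/0.1098] = Φ(1.06) = 0.855

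Exact binomial enumeration of the uncorrected chi-squared test gives 0.869. The stated figure of more than 80% reproduces.

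**2. Literal reading.** For a 2 × 2 table, chi-squared = N(ad − bc)² / (product of the four margins). Take an invented cohort of 28 active and 14 placebo patients, with rows baseline and columns Week 24, each Satisfied then Unsatisfied.

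- [[2, 2], [19, 19]]: ad − bc = 38 − 38 = 0, so p = 1.0. The 21 patients satisfied at Week 24 could split 19/28 active v 2/14 placebo (between-arm chi-squared = 42 × 210² / (28 × 14 × 21 × 21) = 10.7, p = 0.001) or 14/28 v 7/14 (p = 1.0). The shift-table p-value is the same in both cases.
- [[12, 1], [1, 28]]: one patient improves and one worsens, so there is no net change. Chi-squared = 42 × 335² / (13² × 29²) = 33.2, p = 8 × 10⁻⁹.
- If nobody in a cohort is satisfied at baseline, one row is empty and the statistic is undefined.

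**3. Own-cohort reading.** With a patients per active dose, completers total a + a/2 + a + a/2 + a + a/5 = 4.2a. Setting 4.2a = 120 gives a ≈ 28.6, own-cohort placebo of about 14, 14 and 6, and pooled placebo of about 34. Using 28 for every dose is an assumption: SAP 2.6 names 28 for the 12 mg group and expects the other dose groups to be similar. Borrowing the SALT rates as a second assumption, exact power is:

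| Comparison | 35% v 10% | 45% v 10% | 55% v 10% |
|---|---|---|---|
| 28 v 28 pooled | 0.63 | 0.87 | 0.97 |
| 28 v 34 pooled | 0.70 | 0.90 | 0.98 |
| 28 v 14 (Cohort 1 or 2) | 0.44 | 0.70 | 0.89 |
| 28 v 6 (Cohort 3) | 0.13 | 0.38 | 0.62 |

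For 28 v 6 at 45% v 10%, expected responders are 12.6 + 0.6 = 13.2. The smallest expected cell is 13.2 × 6/34 = 2.3, so the chi-squared approximation is itself doubtful there.

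**4. Neutral.** Protocol Appendix 17.3.2 allows a Neutral answer, and the two SAP categories omit it. With invented Satisfied/Neutral/Unsatisfied counts of 10/10/8 v 3/5/20:

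- Neutral counted as not satisfied: 10/28 v 3/28, chi-squared = 56 × 196² / (28 × 28 × 13 × 43) = 4.9, p = 0.027.
- Neutral left out: 10/18 v 3/23, chi-squared = 41 × 176² / (18 × 23 × 13 × 28) = 8.4, p = 0.004.

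**The case against.** The strongest reply is that *cohort* here simply means dose group. Protocol 12.4 says "data will be summarized by active treatment by cohort dose level versus placebo-treated patients", and SAP Section 7 writes "x2 for the 4 mg cohort, x2 for the 8 mg cohort"; both use the word loosely for dose. Table 8-1 calls the item a responder analysis. The Section 3 conventions supply both a treatment dimension and pooled placebo for any summary table, and Section 12 announces no exception. The layout sits in Attachment A, which was not available and may already be right. This makes the benign reading the likely intent, and it stands.

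It does not rescue the sentence. The Section 3 conventions give way wherever something else is specified, and *by cohort* can be read as such a specification. The SAP also treats the two terms as distinct: listings are sorted by cohort within treatment, and analysis populations are summarised by treatment and cohort. Even with *cohort* read as dose, the text attaches the test to the shift table rather than to a responder proportion.

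It is also fair to object that the power figures and example tables measure nothing in this trial. They show only how the readings differ. The placement of Neutral is a secondary wording point, and the documents do not dictate an answer.

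**Conclusion.** The sentence as written specifies the wrong comparison for an exploratory endpoint. Both the literal and the own-cohort readings conflict with SAP 8.4, with SAP Section 3 and with the neighbouring tests in 8.4.2. Severity is low: there is no decision rule, PGI-I and patient VAS-S keep their treatment comparisons, and the likely intent is already correct.

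A reader might infer that the sponsor has chosen a test blind to treatment, or has abandoned pooled placebo for patient-reported outcomes. The documents do not support either. The general rules point the other way, and no exception is declared. Nor is the change from ANCOVA hidden, since Section 12 states it. The shift table as a display suits an endpoint defined as change from baseline and is not at fault. The primary analysis is untouched.

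The conclusion rests on the SAP text alone. If the shell for Table 14.2.4.2 shows treatment groups with pooled placebo and a test of the Week 24 proportion, only the wording needs to be brought into line.

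**What to change.** In SAP 8.4.2:

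- Replace *by cohort* with *by treatment group (placebo pooled)*.
- Apply the SAP's chi-squared test to the proportion Satisfied at Week 24, each dose against pooled placebo.
- Keep the shift table as a descriptive display by treatment group, with no chi-squared p-value on it.
- State in the same sentence how Neutral is counted. Counting it as not satisfied keeps every answering patient in the denominator, but any rule set in advance would do.
- If an own-cohort comparison is really intended, declare it as an exception to SAP 8.4.

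Check the shell for Table 14.2.4.2 against the revised sentence. The cost is one SAP sentence and, at most, a small program change. No new data are needed, and there is no need to return to the protocol's ANCOVA.
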